### **1. Protocol Title:**

Splanchnic Nerve Block for Therapy of Chronic Heart Failure (Splanchnic HF II)

### **2. Purpose of the Study:**

Splanchnic vasoconstriction may contribute to decompensation of chronic heart failure via volume redistribution from the splanchnic vascular bed to the central compartment. This is a sympathetically mediated reflex and can be interrupted through a splanchnic nerve block. Therefore, we hypothesize that interruption of the efferent/afferent innervation of the splanchnic vasculature will decrease cardiac congestion and improve renal function in subjects presenting with heart failure.

Objectives:

1. We will determine if splanchnic nerve blockade decreases cardiac preload as measured by invasive hemodynamics.
2. We will determine if splanchnic nerve blockade will improve invasive hemodynamics during exercise.
3. We will determine if splanchnic nerve blockade improves symptoms of shortness of breath.

### **3. Background & Significance:**

Conventional wisdom dictates that heart failure (HF) exacerbations follow a period of fluid accumulation leading to volume overload. However, study of weight in HF shows that 54% of subjects have an exacerbation without antecedent weight gain. Invasive monitoring of hemodynamics showed that central venous pressure rises in the weeks prior to decompensation despite no weight change in both systolic and diastolic heart failure. The leading theory for explaining this phenomenon of increased central venous pressure in the absence of change in total body water is that subjects with heart failure (HF) have impaired ability to store blood in their splanchnic vascular compartment. In a healthy population, the splanchnic bed contains about 40% of the total blood volume, 80% of which is stored in capacitance veins, and serves as a buffer for the central vascular compartment. Fluid is normally mobilized from this compartment via increased sympathetic tone and circulating catecholamines in response to a variety of physiologic and pathologic stressors. Given the role that the splanchnic circulation plays in hemodynamic regulation, it is hypothesized that increased sympathetic tone in the splanchnic vasculature contributes to both acute and chronic heart failure decompensation by mobilizing fluid to the central vasculature (Fallick C, *Circulation Heart Failure* 2011).

Animal models provide direct evidence of this pathophysiological effect. In healthy animals, splanchnic nerve stimulation shifts blood into the central compartment, increasing preload and cardiac output. In dogs with cardiac pacing induced systolic heart failure, splanchnic vascular capacitance was decreased (Ogilvie RI, *Circulation* 1992). In these dogs, surgical transection of the splanchnic nerve,

terminating sympathetic tone, results in decreased preload as measured by systolic and diastolic pressures and increased compliance of the left ventricle. In humans splanchnic nerve blocks are commonly used for pain control in subjects with intractable visceral organ cancer pain. The nerve blocks are done temporarily using anesthetic agents or more commonly permanently using neurolytic agents. Interestingly, the most common “side-effect” of this therapy includes transient orthostatic hypotension due an increase in splanchnic vascular storage capacity, which typically is prevented by aggressive pre-procedural hydration (Eisenberg E, Anesthesia and analgesia 1995). In a pilot study using a short acting anesthetic agent (lidocaine) we have applied the splanchnic nerve block to acute heart failure subjects and found a reduction in resting cardiac filling pressures and an improved cardiac output (Figure 1 for the first 5 analyzed cases of total 10 subjects done by today). We found also found that the splanchnic nerve block improved shortness of breath and brain natriuretic peptide levels as an indication of cardiac decongestion.

[figure not shown]

Figure 1:  
 Panel A: Role of volume redistribution in the congestion of heart failure.  
 Panel B: Procedural aspects of the splanchnic nerve block intervention.  
 Panel C: Effects of the splanchnic nerve block on intra-cardiac pressures.  
 Panel D: Effects on the splanchnic nerve block on symptoms and biomarker.

In addition to the strong evidence supporting splanchnic nerve blockade as treatment of volume overload, it is possible it will also treat cardiorenal syndrome. The autonomic nervous system plays a critical role in the regulation of the kidney. Though this system is not fully understood, preclinical and clinical studies indicate the presence of a hepatorenal reflex that inhibits the renal function and causes fluid retention. This reflex has its origin in the portal vein and is stimulated by portal congestion. The splanchnic nerves represent the afferent and partially the efferent arm of the reflex arch. Inhibition of this reflex pathway in animals and a small human pilot study was shown to improve renal function and urine production.

#### **4. Design & Procedures:**

This study will be a prospective, uncontrolled clinical trial. The study will not be controlled as invasive monitoring of hemodynamics will be performed, allowing clear demonstration of a cause-effect relationship.

This study aims to piggy-back on an elective right heart catheterization (RHC) in subjects with chronic heart failure. The right heart catheterization will be part of the subject's standard of clinical care (SOC). Subjects eligible for this study will be referred to the Duke cath lab for the evaluation of cardiac filling pressures because it is found to be necessary by the outpatient provider. This will occur in the cardiac catheterization lab. Subjects get scheduled for RHC days to weeks (2-3) ahead of their procedure. The eligible subject will be contacted before the study to be informed about the eligibility for the study and basic information about the study will be provided over the phone shortly after they have been scheduled. Subject will be consented in person in the morning of the procedure.

The subject will undergo pre procedural testing as demonstrated below in the flow chart (all part of the clinical study - CS). Besides the RHC (SOC) the subject will undergo an invasive cardiopulmonary exercise with the RHC in place. Baseline evaluation is followed by a regional nerve block (bilateral splanchnic nerves) while the subject is in the catheterization lab. This will be performed by an anesthesiologist experienced in splanchnic nerve blocks.

Figure 2: Study flow chart

[figure not shown]

Table: Study events

Required Assessment	Pre procedure (day of)	Baseline (intra-procedure)	Block	Post Block Procedure	Recovery	24 h after procedure	48 h after procedure	6 Months after Procedure (±14 days)
Vitals (BP, HR, RR, SpO2)	X (SOC)	X (SOC)	X (SOC)	X (SOC)	X (SOC)			
Weight	X (SOC)				X (SOC)			
Orthostatic vitals	X (CS)				X (CS)			
Urine output (continuous recording)	X (CS)	X (CS)	X (CS)	X (CS)	X (CS)			
Valsalva		X (CS)		X (CS)				
Labs: BMP, pro-BNP, urine sodium,	X (SOC/CS)				X (CS)			
Labs (Angiotensin II), Plasma Metanephrines, Vasopressin, Plasma Catecholamines, Lactate		X (CS)		X (CS)				
Dyspnea Questionnaire		X (CS)		X (CS)	X (CS)	X (CS)	X (CS)	
Six minute walk test	X (CS)				X (CS)			
Impedance and lung fluid content measurement		X (CS)		X (CS)				
Heart rate variability	X (CS)	X (CS)	X (CS)	X (CS)	X (CS)			
Echocardiogram		X (CS)		X (CS)				
Invasive CPX		X (SOC/CS)		X (CS)				
Splanchnic nerve block			X (CS)					
Phone Call						X (CS)	X (CS)	X (CS)

\*Phone call will capture mortality status and number of subject admissions to the hospital since procedure

Following enrollment into the study the subject will undergo the following tests/measurements. A majority of the clinical testing occurs as part of the clinical study (CS) however the main procedure of RHC is standard of care (SOC).

Pre-procedure: Following information will be collected from the subject's charts that will be done as standard of care (SOC). Study specific tests/recordings are also listed below:

- If the subject is female and childbearing potential and has not had a pregnancy test since the arrival to the hospital, a blood pregnancy test will be done (CS). If positive the subject will be excluded from the study.
- Subjects will have strict measurement of urine output (SOC). A urine sample will be sent to the laboratory to check for the sodium concentration (CS). Subjects requiring a foley catheter will have measurements taken at comparable time intervals (SOC).
- Recorded vitals including weight, BP, HR, RR, SPO2 on the day before procedure and within 1h before procedure (SOC) and record heart rate variability using a non-invasive wrist monitor for 5 minutes (CS).
- Orthostatic vitals (5 minutes supine, 1+5 minutes sitting and 1+5 minutes standing) on the day before procedure and within 1h before procedure (CS). Also we will document whether s has symptoms bending over for 10 seconds (bendopnea).
- Labs: Basic metabolic panel (BMP) (SOC), brain natriuretic peptide (BNP) (CS), urine sodium (CS) plasma angiotensin II (CS), plasma arginine vasopressin (CS), plasma catecholamines. This will not require an extra lab draw. Total expected blood loss is <20ml.
- Dyspnea questionnaire using a 7-point Likert scale and Visual Analog Scale (CS)
- Six minute walk test (CS)
- Echocardiogram at baseline and after the block will be performed while the subject is on the cath table (CS). This is considered one continuous echo. This ultrasound test will also be used to look at liver blood flow.
- If the subject is on diuretics medications the scheduling of the medication will be adjusted to minimize interference with the study intervention.
  - The subject will be asked to hold the morning diuretic medication and the morning dose will be given 3 hours after the procedure (CS). This is not expected to provide any risk to the stable chronic heart failure subject, especially since the diuretic medication will be resumed after completion of study that same day.
- Other medications can be continued, unless otherwise specified in the exclusion criteria.

Procedure:

1. Subjects will undergo elective right heart catheterization in the Duke catheterization laboratory lab as ordered by the primary team. A

cardiopulmonary exercise test will be added if not already ordered by the primary provider. Central hemodynamics will be recorded (baseline, prior to nerve block) (SOC). The access site for the right heart catheterization will be radial, brachial or cervical (SOC) to allow a prone positioning of the subject for the splanchnic nerve block described in the next paragraph. Additional baseline RHC numbers will be recorded with legs elevated, which is done to simulate a fluid bolus.

If the subject's hemodynamics provide any other concern for complications related to the splanchnic nerve block (such as underfilling or severe pulmonary hypertension, not related to left heart failure) as determined by the study personnel, the splanchnic nerve block and associated monitoring will not be performed. The subject will be considered a screen failure. Any information and samples collected prior to this will be discarded/destroyed per institutional policies.

Before cardiopulmonary exercise begins, the subject will perform the Valsalva maneuver. The subject will sit up on the catheterization lab table, after the intravenous lines have been placed. The subject will have an empty syringe placed in their mouth. He/she will blow into the syringe for 30 seconds. This is the standardized method for performing the Valsalva maneuver (Saxena, M, Journal of American Heart Association, 2018). The intracardiac pressures will be measured continuously during the 30 seconds. Following the Valsalva maneuver, the subject will be placed supine on the stationary bike for cardiopulmonary exercise. Cardiopulmonary exercise testing will include a 20 W initial steady phase during which RHC numbers will be recorded and echocardiogram with liver blood flow will be obtained. This will take up to 7 minutes followed by quick (every 1 minute increase in 20W) ramp to peak exercise. At peak exercise repeat hemodynamics and echocardiography will be obtained.

Subjects will further be monitored with:

[figure not shown]
- Telemetry (SOC)
- ClearSite/CheetahMedical/Sphygmocor/ReDS for continuous non-invasive hemodynamic/lung fluid content recording (CS)
- Continuous urine output (ml/hour) recording if foley is present (SOC)
- A non-invasive wrist monitor/chest band to monitor the heart rate variability

Baseline hemodynamics and exercise CPX will be performed before and after the nerve block detailed below.

2. Unilateral splanchnic nerve block performed by an anesthesiologist (see images below) (CS). The anesthesiologist will perform a unilateral block to the splanchnic nerve. The blood pressure will be checked, after 15 minutes, post-block. If the systolic blood pressure is reduced by  $> 20$ mmHg, the contralateral splanchnic nerve will not be blocked. Following the right heart catheterization procedure the subject will be prone on the abdomen. Central venous access remains in place. Needle will be placed under fluoroscopic guidance in the posterior chest wall. Anesthetic solution (1.5% lidocaine with 1:200,000 epinephrine and of 0.5% ropivacaine) will be injected. Lidocaine 1.5% with Epinephrine 1:200,000 will be used initially to confirm extravascular administration. The subject will then be placed back on his/her back. The subject will then undergo repeat hemodynamic measurement with the RHC catheter that was already in place. Then the subject proceeds with invasive cardiopulmonary testing after a 30 minute break. The central venous catheter will be removed after the hemodynamic monitoring/testing is completed in the catheterization laboratory.

Additional measurements include:

- Orthostatic vitals (CS).
- Dyspnea questionnaire (CS)
- Echocardiography and liver flow measurements (CS)

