#### Blood samples processing:

Some blood samples collected before and after the nerve block (plasma metanephrines, plasma catecholamines, angiotensin II and arginine vasopressin, lactate) will be processed (centrifuged) and stored at -70 degrees Fahrenheit before sent out to an external lab. Storage

duration may vary between weeks to months. Samples will be stored in a research freezer located on the 7th floor of Duke North (cath lab research freezer). As part of the study, we will send blood for study-related laboratory tests to the Mayo clinic and Inter Science Institute. These would include laboratory tests such as metanephrines, vasopressin, catecholamines, and angiotensin. A data transfer agreement is already in place.

Safety endpoints:

- The duration of the anesthetic block is estimated for 12-24 hours. The subject will be monitored for up to 3 hours in the catheterization laboratory/holding area, if there is any concern or evidence of procedure related complications the will be kept overnight in the cath lab holding area. A potentially observed effect of the block to prevent discharge the day of procedure could be orthostatic hypotension. will also be contacted at 48 hours post procedure to ascertain any potentially missed complications. Further the subject's medical chart will be observed for 6 months following study enrollment to evaluate for admissions for heart failure.

Incidence of major side effects has been reported to be <1:1000 and are expected to occur immediately post nerve block. They include:

- Pneumothorax, possibly requiring a chest tube
- Aortic puncture with retroperitoneal bleed or hemothorax
- Spinal cord trauma with possibly paralysis

Incidence of minor side effects like:

- Orthostatic hypotension
- Pain at puncture site and intercostal neuralgia
- Gastrointestinal dysmotility including diarrhea, constipation and abdominal cramping
- Bleeding at puncture site

Efficacy endpoints:

The following efficacy endpoints will be evaluated:

- Primary:
- Improvement in 20 W and peak exercise PA mean and wedge pressure
  - Reduction in central venous pressure and/or pulmonary artery pressure (diastolic) and/or pulmonary capillary wedge pressure at 30 minutes after nerve block

Secondary:

- Reduction in central venous pressure and/or pulmonary artery pressure (diastolic) and/or pulmonary capillary wedge pressure at 30 minutes after nerve block

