### **Pregnancy**

#### **Procedure**

- Unable to tolerate procedure as determined by subject or investigator
- will be excluded if invasive hemodynamics on study date determine that the subject does not have elevated filling pressures at rest or stress. Following pressures/situations will exclude the subject: wedge pressure <15mmHg (<12mmHg on inotrope) at rest and <25mmHg with peak stress (<22 with inotropes) and greater than the central venous pressure or determined by study personnel to be at risk for nerve block related complications.

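### Invasive monitoring does not make an uncontrolled before/after study show cause and effect: peak pressures also carry any load difference, and wedge carries selection on baseline

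*Combined protocol and SAP*

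**What the plan says.** Section 4 (Design & Procedures) openly declares a prospective, uncontrolled trial and gives the reason: "The study will not be controlled as invasive monitoring of hemodynamics will be performed, allowing clear demonstration of a cause-effect relationship".

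Items 1 and 2 of the procedure in the same section set the sequence. Resting pressures are taken before the block. The first exercise test then has a steady 20 W stage, "followed by quick (every 1 minute increase in 20W) ramp to peak exercise". The text adds: "At peak exercise repeat hemodynamics and echocardiography will be obtained". After the block, resting pressures are repeated through the same catheter. The second exercise test comes later in that session: "Then the subject proceeds with invasive cardiopulmonary testing after a 30 minute break".

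The efficacy endpoints list as primary "Improvement in 20 W and peak exercise PA mean and wedge pressure", together with resting CVP, PA diastolic pressure and wedge at 30 minutes after the block.

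Under Exclusion criteria (Procedure), study-day invasive values remove subjects without raised filling pressures. The excluding values include "wedge pressure <15mmHg (<12mmHg on inotrope) at rest and <25mmHg with peak stress", with a lower peak figure on inotropes.

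Section 14 compares baseline with post-intervention by paired t-test at a two-sided 0.05 level.

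**The concern.** The single arm is not the problem; it is disclosed. The problem is the reason offered for it. Precise measurement removes doubt about whether a pressure changed, not about why. The missing quantity is the second reading the same subject would have had without the block, and nothing in the protocol estimates it.

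Two of the protocol's own procedures make this more than a general remark. First, nothing fixes, matches or adjusts for the load at which the peak readings are taken. Second, the only pre-block readings described both qualify the subject and appear to serve as the baseline of the paired test. If the sentence in section 4 stands, it invites the reader to take the whole paired difference as the block effect, although part of a peak difference could be load and part of a wedge difference could be selection.

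**Working it through.** **The plan's own figure.** Section 14 states power 0.90 for a 25% fall in CVP with 16 subjects but gives no SD. A two-sided paired t-test with n=16 has power 0.90 at a standardised difference of 0.868, so the SD of change would have to be 25/0.868 = 28.8 percentage points. The statement can be neither confirmed nor refuted, and this point does not depend on it.

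**Which endpoint is open to which route.** With no control, observed change = block effect + time and sequence + (pressure-load slope × change in load) + regression to the mean.

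| Reading | Load can differ | Direct cut-off on the baseline value | Time and sequence |
|---|---|---|---|
| Peak wedge | yes | yes | yes |
| Peak PA mean | yes | no | yes |
| Resting wedge | no | yes | yes |
| 20 W wedge, PA mean | no (fixed) | no | yes |
| Resting CVP, PA diastolic | no | no | yes |

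**Rate used below.** The false-reduction rate is the probability that a noncentral t with n−1 degrees of freedom and noncentrality (shift/SD of change)×√n falls below −t(0.975, n−1). With no shift it is 2.5%. n=30 is the enrolment ceiling (section 7); n=16 is from the power statement. All variances, means and slopes are assumptions.

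**Selection.** Read literally, a subject stays if resting wedge is at least 15 or peak wedge at least 25 mmHg. The inotrope thresholds and the unclear comparison with CVP were not modelled. Mid case: candidate means 16.5 (rest) and 26 (peak), true SDs 5 and 7, true correlation 0.7, reading-error SDs 3 and 4, zero block effect. In simulation, wedge falls 0.40 mmHg at rest and 0.43 at peak.
- Rest: SD of change ≈ √2×3 = 4.24; noncentrality −0.40/4.24×√30 = −0.52; rate 7.3% (5.4% at n=16).
- Peak: SD of change ≈ √2×4 = 5.66; noncentrality −0.43/5.66×√30 = −0.42; rate 5.9% (4.7% at n=16).
- If pre- and post-block errors correlate at r, the resting shift scales by (1−r). At r=0.5 it is 0.40×0.5 = 0.2 mmHg (rest and peak 5 to 6% at n=30). At r=0.8 it is 0.40×0.2 ≈ 0.1 mmHg (4%).

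Range over 27 combinations of means and error SDs, independent errors: rest under 0.1 to 1.1 mmHg (3 to 16% at n=30), peak under 0.1 to 1.2 mmHg (3 to 14%), 20 W zero. A second set of assumptions (total SDs 6 and 8, reliability 0.5 to 0.9) gives 0.1 to 1.6 mmHg at rest and 0.1 to 1.8 at peak (4 to 29% at n=30).

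The extreme corner takes low means, the largest errors, errors correlated 0.8 across stages and none between pre and post. It gives 46% and 45% at n=30 for rest and peak, and 37% for 20 W wedge. At pre/post correlation 0.8 these fall to 12%, 12% and 10%.

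**Load.** Suppose wedge rises 10 mmHg over 60 to 100 W. The slope is 10/100 to 10/60 = 0.10 to 0.167 mmHg/W, so one 20 W stage is worth 2.0 to 3.3 mmHg.
- If 25% of subjects stop one stage earlier, mean peak wedge falls 0.5 to 0.8 mmHg. Steep slope, SD of change 4: √(16 + 3.33²×0.25×0.75) = 4.25; noncentrality −0.83/4.25×√30 = −1.07; rate 18%. Shallow slope, SD 6: rate 6%. At n=16 the range is 5 to 11%.
- If 10% do, the fall is 0.2 to 0.3 mmHg (4 to 6% at n=30).
- If 25% go one stage further, mean peak wedge rises 0.5 to 0.8 mmHg. Power at n=30 for a true 3 mmHg fall drops from 98% to 77–90% (SD 4) or from 75% to 46–59% (SD 6).

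**The case against.** The plan has real protections. Both sets of readings come from one session with the catheter left in place, the morning diuretic is held until after the procedure, and subjects started on heart failure drugs in the preceding 48 hours are excluded. These reduce confounding by time; they do not remove it. Much of the primary evidence also escapes the two specific routes: the 20 W stage is a fixed load, and resting CVP has neither a load problem nor a numeric cut-off. No formal decision rule uses the causal sentence, and section 14 speaks only of declaring pre and post values different. All of this stands, and it limits the point to the claim and to the peak and wedge readings.

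A reader might go further and infer that the wedge results are mostly artefact, citing the 46% corner. The documents do not support that. The corner needs several unfavourable assumptions together, including no correlation between pre- and post-block errors. No passage settles that correlation: the catheter stays in, but the subject is turned prone and back.

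A reader might also infer that the second test will stop at a lower load. Nothing in the documents says loads will differ, or in which direction. Finally, that the qualifying readings are the analysed baseline is the natural reading but not a stated fact; Figure 2 is not shown.

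**Conclusion.** Wrong as written. The causal sentence in section 4 does not follow from invasive monitoring, and two of the protocol's own procedures show why.

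The ordinary selection effect on wedge is small: about 0.1 to 0.4 mmHg, with a false-reduction rate of 4 to 7% at n=30 against 2.5%. A load difference could create or hide a change in peak pressure; its sign and size are unknown. Every magnitude rests on assumed variances, means and slopes, and on the qualifying wedge also being the paired-test baseline.

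Resting CVP and the 20 W readings have only the general limit of a single-arm study, apart from any selection they inherit through correlation with the gated wedge values. It would be too strong to conclude that the design is unusable or that a large fall in wedge could not reflect the block.

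**What to change.** 1. Replace the causal sentence in section 4 with: *Changes are before/after differences within subjects; effects of sequence, time and regression to the mean cannot be separated from the block without a control.*
2. Make the fixed 20 W stage, already in the primary endpoint, the main exercise comparison. Record the watts at each peak reading. Report peak wedge and PA mean as supportive results, alongside the within-subject change in load.
3. State selection on baseline wedge as a limitation of the wedge results.

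Do not add a rule that blocks or permits attribution to the block according to mean peak load. With no tolerance, one subject in 30 stopping one stage early lowers the mean by 20/30 = 0.67 W, worth about 0.67×0.167 = 0.11 mmHg, yet would block attribution of a fall of any size. If 10 to 25% of subjects change stage with no systematic difference, such a rule would fire in 38 to 43% of trials at n=30 (33 to 40% at n=16). It would also condition on a quantity that the block may itself change.

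Cost: items 1 and 3 are wording. Item 2 adds one recorded number per peak reading and a change of emphasis, with no extra hemodynamic readings and no data discarded. The downside is a narrower claim and less weight on peak pressures; the selection effect is disclosed, not removed.

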#### Follow up procedures:

Following right heart catheterization and lidocaine splanchnic nerve block the will be observed for monitored in the cath lab holding area for 3 hours following nerve block (SOC).

- Continuous recording of urine output for the procedure day (CS) will be achieved by recording urine output at the beginning of pre-testing, just before the cath lab procedure, just after the cath lab procedure and before the subject leaves home.
- Basic vitals (SOC) and orthostatic vitals (CS) following the cath lab procedure and record heart rate variability using a non-invasive wrist monitor (CS).
- Repeat labs after the procedure before the subject leaves. Pro-BNP, BMP, serum sodium (all CS)
- Labs: Angiotensin 2, plasma metanephrines (if on inotropes), plasma catecholamines, vasopressin, lactate, and urine sodium will be collected immediately before and after the procedure
- Dyspnea questionnaire after nerve block (CS) and again at 48 hours
- Six minute walk test (CS) after the block
- Weight after the procedure.

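### The last urine reading and repeat labs are tied to departure, not to the delayed diuretic dose, so diuretic urine can enter a secondary endpoint in subjects who stay on

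*Combined protocol and SAP*

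**What the plan says.** All references are to the combined protocol and SAP.

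- **Diuretic rule (section 4, pre-procedure list).** For subjects on diuretics, "the scheduling of the medication will be adjusted to minimize interference with the study intervention". The morning dose is held and "the morning dose will be given 3 hours after the procedure (CS". The reassurance on safety adds that "the diuretic medication will be resumed after completion of study that same day".
- **Urine output.** The pre-procedure list states: "Subjects will have strict measurement of urine output (SOC". Under Follow up procedures, "Continuous recording of urine output for the procedure day (CS) will be achieved by recording urine output at the beginning of pre-testing", and then "just before the cath lab procedure, just after the cath lab procedure and before the subject leaves home". That makes four readings, the last at departure. The monitoring list in section 4 provides continuous recording only when a Foley catheter is in place, and section 11 makes the Foley optional.
- **Labs.** Under Follow up procedures: "Repeat labs after the procedure before the subject leaves". These include pro-BNP and the metabolic panel. The study events table places them, and the late urine recording, in the Recovery column without a clock time.
- **Length of stay.** Routine subjects are "monitored in the cath lab holding area for 3 hours following nerve block (SOC". The Safety endpoints text allows an overnight stay for any procedure-related concern and names orthostatic hypotension as a possible bar to same-day discharge.
- **Endpoint and analysis.** Urine output in ml/hour, BUN, creatinine and pro-BNP are secondary endpoints. The window for urine output and renal function is described only as a period of hours after the procedure. Section 14 compares baseline with post-intervention values by paired t-test. Section 4 describes the trial as uncontrolled.

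**The concern.** The diuretic rule exists to keep the drug out of the measurements, so the intended order is measurements first, diuretic second. The dose and the measurements nevertheless run on different clocks. The dose is fixed at 3 hours after the procedure, while the last urine reading and the repeat labs are fixed only by departure. In a subject kept longer, the dose can come first.

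Diuretic urine in the last interval raises post-block output, which is the direction the sponsor hypothesizes, and there is no control arm to expose it. A long stay can also be a consequence of the block itself, through orthostatic hypotension, so the affected subjects need not be a random subset. Pro-BNP, BUN and creatinine could also be affected if drawn after the dose, but no direction is claimed for them.

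**Working it through.** The plan gives no figure for urine output to reproduce. Its only computed figure is the power statement for central venous pressure in section 14, which does not bear on this point. The check is therefore a comparison of clocks, followed by simple arithmetic.

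**Step 1. Routine path.** Observation ends 3 hours after the block (Follow up procedures). The dose is due 3 hours after the procedure (section 4). The block is followed by repeat hemodynamics, a 30-minute break and a second exercise test. If the procedure includes these steps, the dose falls after planned observation has ended. If it is counted from the block, the two coincide. Either way, a subject who leaves at 3 hours contributes no diuretic effect: bias 0.

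**Step 2. Extended stay.** A diuretic user kept past the dose, and given it, has a final interval running from the reading just after the cath lab procedure to the reading at departure. That interval contains the dose. No reading is scheduled at the dose. Without a Foley, or a volume recorded at that time, the pre-dose part may not be recoverable.

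**Step 3. Effect on one subject's rate.** Suppose the diuretic adds D ml/hour for up to 6 hours, the subject stays s hours past the dose, and the post-procedure window is 3 + s hours (all assumptions). The excess in that subject's rate is

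X = D × min(s, 6) / (3 + s).

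| s (hours) | X |
|---|---|
| 0 | 0 |
| 1 | D × 1/4 = 0.25D |
| 3 | D × 3/6 = 0.50D |
| 12 | D × 6/15 = 0.40D |

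The documents give no value for D, so X stays a symbol.

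**Step 4. Effect on the mean change.** With k affected subjects among n, the shift is kX/n. The enrolment target is up to 30, with 15 in each heart failure group (section 7). All are taken to contribute urine data, and the values of k are assumptions.

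| n | k | Shift in mean change (ml/hour) |
|---|---|---|
| 30 | 1 | 1/30 × X = 0.033X |
| 30 | 3 | 3/30 × X = 0.10X |
| 30 | 6 | 6/30 × X = 0.20X |
| 15 | 1 | 1/15 × X = 0.067X |

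This describes the mean only. A few outlying values also widen the standard deviation, so nothing is claimed about the p-value.

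**The case against.** The strongest reply is that the plan already states the order: the diuretic is resumed once the study is complete. On a natural reading, the day's assessments are finished before the dose. This does show intent. But the sentence is given as a reassurance about safety. It does not say that completion means the last urine or lab sample, and it changes neither the 3-hour dose nor the departure-based readings.

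The second reply is that harm needs a chain of exceptions: a diuretic user, kept past the dose, who still receives it, has no separable volume, and has the late urine counted in the endpoint. Most of this stands as a limit on size:

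- In orthostatic hypotension, the one reason named for preventing same-day discharge, the dose may well be withheld.
- The call for strict measurement, and the table's reference to continuous recording, may yield a usable volume in some subjects, although neither schedules a reading at the dose.
- A next-morning reading may not belong to a procedure-day window at all. The text does not settle this, and that is itself part of the gap.
- The labs can be drawn during routine observation, before the dose. Nothing requires it in subjects who stay.

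Finally, the study flow chart (Figure 2) is not available in the text reviewed and might show the order. The conclusion rests on the visible text.

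**Conclusion.** The concern holds, as a minor point with medium confidence. The order the sponsor intends is not secured for diuretic users who remain in house when the dose is due. The effect is zero for a subject who leaves at 3 hours. Otherwise the mean change in urine output shifts upward by kX/n, with both k and X unknown from the documents. Bias arises only if the dose is actually given and the later urine is counted in the endpoint. It is confined to secondary endpoints, because the primary hemodynamic measurements are made in the catheterization laboratory before the dose. It is still worth correcting: without a volume recorded at the dose, the analyst may have no means of removing diuretic urine later.

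**What to change.** For diuretic users still in house when the dose is due, add two or three sentences to Follow up procedures:

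1. Take the final endpoint urine volume (a timed void if there is no Foley) and the repeat pro-BNP and metabolic panel immediately before the dose.
2. Record the time of the dose, or that it was withheld.
3. End the urine-output endpoint window at the dose, and report later urine descriptively only.

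The dose time itself stays as written, so no treatment is delayed. The cost is the added text, one time field and one timed void. The downside is a shorter urine window in subjects who stay longer.
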